Prostate Volume ^e Measurement (via ultrasound)		X ^e											
Uroflowmetry	X											X	
Urodynamics ^f		X						X					
Laboratory Assessments ^g	X		X			X		X				X	
Dispense Bladder Diary ^h	X	X	X		X	X	X	X		X			
Dispense Run-in Study Drug		X											
Dispense Double-blind Study Drug ⁱ			X			X	X	X		X			
Administer Witnessed Dose of Study Drug		X	X										

AE = adverse event; BPH = benign prostatic hypertrophy; ECG = electrocardiogram;

IPSS =

International Prostate Symptom Score; IWRS = interactive web response system; OAB = overactive bladder;

PGI =

Patient Global Impression; PRO = patient-reported outcomes; PVR = Post-void residual; SAE = serious adverse event; WD = withdrawal

NOTE: Certain study assessments and procedures also may be performed remotely to minimize contact, as outlined in Section 8.6.

* To account for additional time that may be necessary to ensure safety through COVID-19 preventive measures, a COVID Mitigation Window, with extended windows for visit timings, has been implemented. However, if safe and feasible, study visits should adhere to the schedule outlined Visit Window when.

a With the exception of prostate volume measurement (which can be completed any time prior to randomization), all Screening procedures and the initial 3-day Bladder Diary must be completed prior to Run-In (Visit 2).

b The Safety Follow-up is not applicable for subjects who enter the extension study (URO-901-3006).

- d Vital signs (including blood pressure [triplicate], pulse, body temperature, respiration rate, and weight) should be taken prior to blood draws and study drug dosing; height is measured at Screening only.
- e A historical prostate volume measurement by ultrasound, performed within 12 months prior to the first day of Screening, is acceptable if the criteria detailed in [Section 8.3.8](#) are satisfied. For subjects with no acceptable historical measurement, a prostate volume measurement by ultrasound must be completed prior to randomization (Baseline/Visit 3).

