- f Urodynamics procedure only applies to the Urodynamics sub-study of 60 subjects. Subjects will provide an additional urodynamics sub-study consent at Screening. A historical urodynamics assessment, performed at the site within 6 months prior to screening, will be acceptable. For subjects with no acceptable historical trace, a urodynamics assessment must be completed prior to randomization (Baseline/Visit 3). The Week 12 urodynamics assessment may be conducted on a different day than the Week 12 visit if it is done within the ± 4 day visit window. All assessments (historical/ Baseline and Week 12) must be performed using the same urodynamics equipment and procedure (fill rate, catheter size, fluid, etc).
- g Blood draws should be performed after all PRO and vital sign assessments. Refer to [Section 10.2](#) for a list of laboratory assessments performed.
- h Refer to [Table 1](#) for details on when subjects should complete the Bladder Diary for each study timepoint. Note that the Bladder Diary may be dispensed or returned remotely (ie, delivered by mail, courier, or curbside pickup) and may be dispensed at an earlier timepoint. If dispensing in-person, ensure an adequate supply of diaries is provided (eg, diaries to be completed by the subject prior to Week 2 are dispensed at Baseline, and diaries to be completed by the subject prior to Week 16 and Week 20 are dispensed at Week 12).
- i For visits that occur after Baseline, double-blind study drug may be dispensed to the subject by means other than by in-person contact (eg, via curbside pickup, trackable courier, or another method approved by the Sponsor/CRO).

Table 1 Bladder Diary Completion Schedule

Diary Completion Timepoint	Run-In	Baseline	Week 2	Week 4	Week 8	Week 12	Week 16	Week 20	Week 24 (Day 169)
Begin 3-day Diary	At least 3 Days prior to Run-In Visit	3 to 7 Days prior to Baseline Visit	Day 8 to 12	Day 22 to 26	Day 50 to 54	Day 78 to 82	Day 106 to 110	Day 134 to 138	Day 162 to 166
Acceptable completion window	After Initial Screening Visit and prior to Run-In Visit	7 Days prior to Baseline Visit	Days 8 to 14	Days 22 to 28	Days 50 to 56	Days 78 to 84	Days 106 to 112	Days 134 to 140	Days 162 to 168

NOTES:

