8.2.1. Bladder Diaries

The Bladder Diary is used by subjects to record the frequency of daily OAB symptoms including all micturitions, urgency, incontinence, nocturia, one 24-hr volume voided of urine, and main reason for incontinence, and volume voided per micturition (over one 24-hour period) by selecting the respective box for each symptom occurring during the course of a given day and night. To minimize unnecessary on-site contact and ensure that the subject has a basic understanding and ability to comply with completion of the diary, an optional prescreening diary may be provided to potential study subjects prior to completion of screening procedures.

A schedule of completion timelines for the Bladder Diaries for each associated visit is provided in [Table 1](#). The Bladder Diary should be completed by the subject on 3 consecutive days within the 7 days prior to each Bladder Diary Completion timepoint as outlined in [Table 1](#). Urine volume may be collected during any one (1) of the Bladder Diary Days, and it should be recorded for ~24 hours starting from the time the patient gets up for the day and continues until the time the patient gets up for the day on the next day.

A “Diary Day” is defined as the time between when the subject gets up for the day each morning (ie, the time the subject got up for the day yesterday to the time the subject got up for the day today; approximately a 24-hour period).

To be eligible for the study, subjects must have a minimum of:

- 3 consecutive Diary Days during the Screening Period (prior to the Run-in Visit), and
- 3 consecutive Diary Days during the Run-in Period (over the 7 days prior to the Baseline Visit), and
- be capable in the investigator's opinion of maintaining compliance with the diary requirements, including the measurement and recording of urine volume, as required, at Baseline and throughout the course of the study.

At all study visits, the site staff should inquire whether the subject had any difficulties with the diary and address any questions subjects may have. Instructions for proper completion of the diary should be re-reviewed. Subjects will be trained to enter data immediately following each event (in real time) and to input data from any "missed" events as soon as they are able. They will review and confirm that data from all events occurring within the preceding Diary Day (approximately 24 hours) have been entered at a consistent time each morning (eg, upon getting up for the day).

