9.2. Sample Size Determination

Approximately 1088 subjects will be randomized in a 1:1 ratio to receive one of the following study treatments:

- Vibegron 75 mg tablet (N = 544)
- Matching placebo tablet (N = 544)

Approximately 544 subjects each will be assigned to the vibegron and placebo treatment groups. Assuming a total of 15% of subjects will discontinue prior to Week 12 (for any reason), there will be approximately 462 evaluable subjects in the vibegron and placebo treatment groups (924 subjects total) at the end of Week 12. The study has approximately 94.3% power to detect a between-group treatment difference of 0.46 in change from baseline in micturitions at a 2-sided 0.05 level assuming a variability estimate of 1.972 based on vibegron Study MRK-008 data and the FDA's statistical reviewer of mirabegron NDA data showing that the micturition treatment effect in men taking 50 mg of mirabegron is 70% of the overall 50 mg of mirabegron population. Additional details are provided at the end of this section.

For the second co-primary endpoint, 462 evaluable subjects per treatment group has approximately 90% power to detect a between-group treatment difference of 0.60 in change from baseline in urgency episodes at a 2-sided 0.05 level assuming a variability estimate of 2.811 based on vibegron Study MRK-008 data and the FDA's statistical reviewer of mirabegron NDA data. Additional details are provided at the end of this section.

The overall study power will be more than 84% with the co-primary endpoints based on the Bonferroni inequality (ie, for any events A and B, $P(A \cap B) \geq P(A) + P(B) - 1$).

Derivation of Estimated Treatment Effect in Men

Based on the published results of the Phase 2 trial of mirabegron and the FDA statistical reviewer of the OAB NDA, we estimated the following:

- The Phase 3 results will have at least 85% of the treatment difference of the Phase 2 results
- The treatment difference for men is at least 70% of the effect of the general OAB population

Table 3 summarizes this information and sources.

Table 3. Data and Sources Supporting Study Sample Size Calculations

Mirabegron Results			
	N	PBO Adj CFB	
Study	Overall	Men	Overall
178-CL-046	473	133	-0.6
178-CL-047	425	116	-0.61
		Simple Average	-0.61

	Phase 2 Micturition PBO Adj CFB	Phase 3 Micturition PBO Adj CFB	Phase 3 as a % of Phase 2
Comparing Phase 3 to Phase 2	-0.64	-0.605	94.5%

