10.7.2. Run-in, Visit 2 (Day -14 ± 4 days)

- Assess inclusion/exclusion criteria
- Review concomitant medications*
- Review AEs/SAEs*
- Review and data enter completed Bladder Diary*
- Record blood pressure (3 results taken 1-2 minutes apart after sitting for 5 minutes), pulse, respiration, temperature, and weight (Part 2 subjects only)
- Record respiration, temperature, and weight at Hour 0, and record triplicate orthostatic blood pressure (sitting blood pressure taken 1-2 minutes apart after sitting for 5 minutes, standing blood pressure taken 1-2 minutes apart within 3 minutes of standing) and orthostatic heart rate (by pulse) measurements at Hour 0 (pre-dose) (Part 1 subjects only)
- Measure post-void residual volume
- Dispense study drug for single-blind Run-in Period
- Administer witnessed dose of study drug (Part 1 subjects only)
- Dispense Bladder Diary*
- If not collected previously (and not available within 12 months of Screening), collect prostate volume (in mL) via ultrasound any time prior to randomization

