4.2.4.2. Analysis Visit Windows

Analysis visit windows for both diary and non-diary data are defined as shown in Table 3. All observations will be given an analysis visit, assigned based on relative study day, as defined in section 4.3.3. If fewer than three diary days are within the analysis window, only the data within the window will be used to calculate visit-level averages. Unless otherwise noted, all data will be listed.

Table 3: Analysis Window Slotting

Analysis window label	Nominal visit	Nominal day	Non-Diary Visit Window	Diary Visit Window
Screening	Visit 1	-49 to - 21	date of informed consent to date of first run-in dose	
Run-in	Visit 2	-14	date of first run-in dose to day -1	7 days prior to date of first run-in dose
Baseline	Visit 3	1	[-1,1]	date of first run-in dose to day -1
Week 1	Visit 4	8	[2, 11]	
Week 2	Visit 5	15	[12, 22]	[7, 18]
Week 4	Visit 6	29	[23, 42]	[19, 39]
Week 8	Visit 7	57	[43, 70]	[47, 67]
Week 12	Visit 8	85	[71, 98]*	[68, 102]
Week 16	Visit 9	113	[99, 126]	[103, 123]
Week 20	Visit 10	141	[127, 154]	[131, 151]

Analysis window label	Nominal visit	Nominal day	Non-Diary Visit Window	Diary Visit Window
Week 24	Visit 11	169	[155, last dose date + 5]	[159, 179]
Follow-Up for Early Withdrawals	NA	NA	>Last dose date + 5	
Follow-Up for Completers	NA	NA	>Last dose date + 5	

*Urodynamics window for Week 12 is [57, 113]

For subjects who withdraw early, assessments taken at the end of study visit will also be summarized with scheduled data if they fall within an on-study visit window and are within 21 days after the last treatment date.

For parameters which were **not** scheduled to be collected at all visits, still use the all-inclusive visit intervals defined for all visits (i.e., the window defined above) to slot records. However, if a value is slotted to a visit unscheduled for a parameter, it will not be summarized (and not be included in the efficacy datasets) but will be included in data listings.

1. If after all records have been slotted, there are multiple valid records within a visit, use the record by the following the rules below:
 - If there are more than three bladder diary days within the window, the three days closest to the nominal visit day will be used to calculate analysis visit averages. If two days are equidistant to the nominal visit day, the earlier day will be selected first.

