6.1. Co-Primary Endpoint Analysis

6.1.1. Primary Analysis

The primary analysis will be based on the FAS. Descriptive summary for observed and CFB will be provided by visit and treatment for both co-primary endpoints. Refer to parameter derivations from Bladder Diary data on Section 4.3.1.

Co-primary 1: CFB to Week 12 in average number of daily micturition episodes

For the assessment of difference between the treatment groups in change from baseline to Week 12 in average number of daily micturition episodes, a mixed model for repeated measures (MMRM) will be used incorporating on-treatment values at all time points (Weeks 2, 4, 8, 12, 16, 20, and 24). The model takes account of any correlation within the same subject over time by using all available data on the subjects. With the assumption of missing at random (MAR), this approach will provide unbiased estimates of treatment effects derived from the model.

The MMRM model will include terms for treatment, visit, baseline value (average number of daily micturition episodes), alpha blocker use with or without 5-ARI (with vs. without), baseline urinary incontinence (yes vs. no), region (US vs. non-US), and interaction of visit by treatment. Stratification factors as randomized will be used in the model. The Kenward-Roger adjustment will be used with restricted (or residual) maximum likelihood (REML) to make statistical inference. An unstructured covariance matrix will be used to model the correlation among repeated measurements. If the unstructured covariance model fails to converge with the default Newton-Raphson algorithm, the Fisher scoring algorithm will be used to provide initial values of the covariance parameters. In the rare event that none of the above methods yield convergence, the following structures will be investigated: heterogeneous Toeplitz, Toeplitz, heterogeneous First-Order Autoregressive [AR (1)], heterogeneous compound symmetry (HCS), and compound symmetry (CS). The covariance structure converging to the best fit, as determined by Akaike's information criterion (AIC), will be used.

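### Optional precision gain: the diary-based efficacy models could also adjust for the mandatory Screening diary, which the plan uses only for eligibility

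*Protocol*

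**What the plan says.** **The Screening diary.** Footnote a to the Part 2 schedule (Protocol 1.4) states that, prostate volume apart, "all Screening procedures and the initial 3-day Bladder Diary must be completed prior to Run-In (Visit 2". Protocol 8.2.1 makes it an entry condition: a man needs "3 consecutive Diary Days during the Screening Period (prior to the Run-in Visit", and a further three Diary Days in the Run-in Period. Inclusion criteria 10 and 12 test the micturition, urgency and nocturia averages at both Visit 2 and Visit 3. Protocol 10.7.2 lists for Visit 2 "Review and data enter completed Bladder Diary". Both pre-randomisation averages should therefore be in the database for every correctly randomised man.

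**The models.** SAP 4.3.4 takes the diary baseline from the Baseline window alone, and SAP Table 3 starts that window at the first run-in dose. SAP 4.3.1 derives the efficacy parameters for baseline and Weeks 2 to 24. SAP 6.1.1 states: "The MMRM model will include terms for treatment, visit, baseline value (average number of daily micturition episodes", followed by 5-ARI stratum, incontinence stratum, region and visit by treatment. The urgency model adds the micturition stratum. SAP 6.2 applies the urgency model to the secondaries, dropping the incontinence stratum for urge incontinence. None of these models has a Screening term.

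**The window.** SAP Table 3 slots the diary reviewed at Visit 2 only if it falls in the "7 days prior to date of first run-in dose". The completion cell in Protocol Table 1 accepts it "After Initial Screening Visit and prior to Run-In Visit".

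**Power.** Protocol 9.2 claims "approximately 94.3% power to detect a between-group treatment difference of 0.46" in micturitions, "at a 2-sided 0.05 level assuming a variability estimate of 1.972". It claims about 90% for an urgency difference of 0.60 with SD 2.811, both with 462 evaluable men per arm, and joint power above 84%.

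**The concern.** A 3-day average is a noisy measure of a man's usual level. A second average of the same quantity, taken before treatment, can explain Week 12 variation that the first one misses. The trial requires and enters that second measure, but no efficacy model uses it, so the residual variance may be larger than it needs to be.

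Both co-primaries must succeed, and the secondaries are tested only if they do, so a modest gain in precision is useful, most of all for urgency, the weaker of the two. The same reasoning extends to IPSS Storage, because IPSS is collected at both Screening and Baseline.

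**Working it through.** **1. The plan's own figures.** Two-sample t test, n = 462 per arm, two-sided 0.05, noncentrality = difference / (SD × √(2/n)).

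- Micturitions: 0.46 / (1.972 × √(2/462)) = 0.46 / 0.1297 = 3.55, power 94.3%.
- Urgency: 0.60 / (2.811 × √(2/462)) = 0.60 / 0.1850 = 3.24, power 90.0%.
- Joint bound: 0.943 + 0.900 − 1 = 84.3%.

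All three agree with Protocol 9.2.

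**2. Variance removed by the Screening average.** Let B, S and W be the Baseline, Screening and Week 12 averages. With B in the model, change from baseline and the Week 12 value have the same residual variance. The ratio of residual variances with and without S is

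(1 − R²) / (1 − r_BW²), where R² = (r_BW² + r_SW² − 2 r_BW r_SW r_SB) / (1 − r_SB²).

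The documents give none of these correlations, so the values below are assumptions.

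- *Equal correlations.* At 0.5, R² = 0.333 and the ratio is 0.667 / 0.750 = 0.889, a cut of 11.1%. At 0.3 the cut is 5.3%; at 0.7 it is 17.0%.
- *Equal correlations, with the entry limits applied to both diaries by simulation.* Correlations of 0.4 to 0.7 before selection give cuts of about 5.5% to 14%. The means and SDs were illustrative: 11 and 3 for micturitions, 6 and 3.5 for urgency.
- *Correlation decaying with time.* With r_BW = 0.5, r_SB = 0.6 and r_SW = 0.45, R² = 0.285 and the ratio is 0.715 / 0.750 = 0.953, a cut of 4.7%. With r_SW = 0.40 the cut is 2.1%. Repeating this pattern for r_BW from 0.3 to 0.7 gives about 1% to 5%.
- *Limit.* If r_SW = r_BW × r_SB, Screening adds nothing once Baseline is known, and the cut is 0%.

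**3. Power if the stated SDs are residual SDs after baseline adjustment (an assumption).** Replace SD by SD × √(1 − cut).

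| Variance cut | SDs used | Micturitions | Urgency | Joint bound |
|---|---|---|---|---|
| 0% | 1.972 / 2.811 | 94.3% | 90.0% | 84.3% |
| 2% | 1.952 / 2.783 | 94.7% | 90.6% | 85.3% |
| 5% | 1.922 / 2.740 | 95.3% | 91.4% | 86.7% |
| 10% | 1.871 / 2.667 | 96.2% | 92.7% | 88.9% |
| 15% | 1.818 / 2.592 | 97.0% | 94.0% | 91.0% |

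**4. Power if the stated SDs are raw SDs of change.** The baseline covariate has then already removed some variance, and the starting point is higher. Simulations calibrated to the stated SDs used diary SD 0.7-1.3 (urgency 1.0-1.8), between-man SD 2-3 (2.5-3.5) and Screening-to-Baseline drift SD 0-1.2 (0-1.7). They gave about 94.4-96.4% and 90.1-93.2% with the baseline value alone. One high-noise micturition case (between-man SD 2, diary SD 1.3, drift SD 0.6, mean 11.5) moves from 96.3% to 97.7% when Screening is added.

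**The case against.** **The plan is sound as it stands.** The models already adjust for the continuous baseline of the same endpoint, strata and region, and the power figures reproduce without a further covariate. A reader might infer that the co-primaries are underpowered or the primary analysis defective. The documents do not support that: the figure of more than 84% is a lower bound, and under independence joint power would be 0.943 × 0.900 = about 85%. This part of the objection stands.

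**The size is unknown and may be small.** The Screening diary can be done at any point in a window that opens at Day -49. It also precedes a placebo run-in that Protocol 4.2 uses to assess placebo response and give diary practice. The Baseline diary is taken after that and may predict Week 12 better, which favours the decaying case. A reader might want to quote a typical gain of 5-10%, or about 11% more patients for nothing. Such figures depend on the assumed correlations, and the documents give none.

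**The window mismatch affects no result now.** It might be read as a loss of efficacy data, but no planned efficacy analysis uses this diary. The protocol is also mixed: the note under Table 1 and a sentence in 8.2.1 refer to the 7 days before each timepoint, as the SAP does. The mismatch matters only once the diary becomes a covariate.

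**It is more than a SAP edit.** Protocol 9.4.2.2 itself lists the co-primary model terms, so the change departs from the protocol. This also stands and is reflected in the fix.

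**Conclusion.** This is a free improvement, not an error. The mandatory, data-entered Screening diary is left out of every efficacy model, and including it would leave the treatment effect that the linear model estimates unchanged. The planned analysis is valid and its stated co-primary power is correct.

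The likely reduction in residual variance is about 1-5% if correlation decays with time, and up to about 15% if the diaries are about equally correlated. On the residual-SD reading, cuts of 2% to 5% raise the joint bound from 84.3% to between 85.3% and 86.7%. On the raw-SD reading, power before the addition is already somewhat above 94.3% and 90%. No gain has been calculated for the secondaries, including IPSS Storage; for them the argument is one of principle only.

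**What to change.** Before unblinding:

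1. In SAP 4.3.1, derive the Screening (Visit 2) diary averages with the same algorithm as the other visits. Widen the Run-in diary window in SAP Table 3 to match the Protocol Table 1 cell, any time after the Screening Visit and before Run-in. Note that the Table 1 note and Protocol 8.2.1 also mention 7 days.
2. In SAP 6.1.1 and 6.2, add the Screening average of the same parameter as a second continuous covariate beside BASE; for IPSS Storage, use the Screening IPSS Storage score. Keep the Baseline diary as the baseline for change, and do not average the two diaries, which would alter the endpoint. Fill a rare missing Screening value with the overall mean.
3. Carry the term into the ANCOVA with multiple imputation (6.1.2.2), both imputation steps in Appendix 11.1, and the subgroup models (6.1.3). Record the departure from Protocol 9.4.2.2 in SAP section 9.

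The sponsor can size the gain on blinded pooled data by fitting the models without treatment, with and without the Screening average, and comparing residual variances. Leaving treatment out matters little: at the planned micturition effect it adds (0.46/2)² = 0.053 to a variance of 1.972² = 3.89, or 1.4%.

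The cost is one derived variable per endpoint and the alignment work above. No new data, visits or patients are needed.

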2.1. Study Rationale

Vibegron is currently in Phase 3 clinical development for the treatment of overactive bladder (OAB) in women and men. This study is intended to evaluate use of vibegron for the treatment of persistent OAB symptoms in the subpopulation of men with benign prostatic hypertrophy (BPH) on pharmacological therapy.

Men with OAB symptoms associated with BPH represent an OAB subpopulation that has not been extensively studied. Oftentimes in these patients, OAB symptoms remain inadequately addressed despite treatment for their BPH (ie, alpha-blocker with or without 5 α -reductase inhibitors [5-ARIs]). For reasons described below, this population warrants specific clinical studies to adequately evaluate and address their unique medical needs. Study URO-901-3005 is designed to be a large (planned N = 1088 subjects), Phase 3, randomized, double-blind, placebo-controlled, parallel-group, multicenter study to evaluate the safety, tolerability, and efficacy of vibegron (75 mg once daily [QD] administered for 24 weeks) in men with symptoms of OAB (ie, ≥ 8 and ≤ 20 micturition episodes per day and urgency episodes of ≥ 3 per day) on pharmacological therapy for BPH.

